#### Management of nausea and vomiting

Nausea and vomiting may significantly affect patients' adherence to the treatment and their quality of life. In order to reduce the occurrence and the intensity of emesis, the patients should be treated according to the recommendation given in Table 4.2.3: 1.

Table 4.2.3: 1 Management of nausea and vomiting

CTCAE Grade	Antiemetic treatment
Nausea = grade 1 and Vomiting = grade 0	No antiemetic treatment unless judged necessary by investigator
Nausea = grade 2 and Vomiting = grade 0	Antiemetic treatment   Pause BIBW 2992 and/or TMZ treatment if grade 2 vomiting or grade 2 nausea persist for 7 or more consecutive days despite optimal supportive care. Resume treatment when CTCAE grade $\leq 1$ .
Nausea = grade 0, 1 or 2 and Vomiting = grade 1 or 2	Antiemetic treatment 
Vomiting $\geq$ grade 3 or Nausea $\geq$ grade 3	Pause BIBW 2992 and/or TMZ treatment

	until return to CTCAE grade $\leq$ 1 or baseline  .
--	-----------------------------------------------------------------

1 Antiemetic treatment should follow the recommendations given in the Consensus Statement of the Antiemetic Subcommittee of the Multinational Association of Supportive Care in cancer (MASCC): Prevention of chemotherapy- and radiotherapy-induced emesis: Results of the Perugia Consensus Conference (R06-0986).

2 Baseline is defined as the CTCAE grade at the start of treatment.

After a treatment pause the dose of BIBW 2992 should be reduced according to the dose reduction scheme in Table 4.1.4.1.2: 1. The occurrence of nausea and/or vomiting and the outcome of treatment will be recorded in the AE section of the eCRF. Antiemetic treatments should be documented in the concomitant medication section of the eCRF with the start and end of treatment dates and daily dose. In case of nausea and/or vomiting  $\geq$  CTCAE grade 2, appropriate hydration (1.5 L/m^2/day plus hydration deficit) must be ensured.

### Management of rash and acne

A proactive and early approach to management of rash is crucial. Rash can be managed by a variety of treatment options to relieve symptoms and improve the rash.

General/Prevention: strict sun protection; use of a sunscreen of SPF 15 or higher, preferably containing zinc oxide; use of a thick, alcohol-free emollient cream; avoid harsh detergents, avoid using a solarium.

- CTCAE Grade 1 rash: mild rash may not need treatment. However, if treatment is considered necessary, topical hydrocortisone (1% or 2.5%) cream and/or clindamycin 1% gel can be used.
- CTCAE Grade 2 rash: relief from major symptoms caused by CTCAE Grade 2 skin adverse reaction should be achieved by a combination of local and systemic therapies including:
  - 1) Systemic antibiotics (doxycycline or minocycline etc.)
  - 2) Topical treatment (hydrocortisone 2.5% cream, clindamycin 1% gel, pimecrolimus 1% cream) and/or antihistamines (diphenhydramine, etc.)
  - 3) Oral prednisone (short term i.e.<14 days treatment) may be added at investigator's discretion.

Systemic and topical treatment should be initiated at the start of CTCAE Grade 2 rash and continue until improvement or resolution to CTCAE Grade  $\leq$  1 or baseline.

- CTCAE Grade 3 (or greater) rash: may be treated in a manner similar to CTCAE Grade 2 rash. However, if CTCAE Grade  $\geq$  3 rash persists despite optimal supportive care (including systemic antibiotics), treatment with BIBW 2992 and/or TMZ should be discontinued until recovery to  $\leq$  CTCAE Grade 1 rash or baseline CTCAE Grade (whichever is higher).

Thereafter patients can resume BIBW 2992 treatment at the next lower dose level as outlined in Section 4.1.4. If CTCAE Grade $\geq$ 3 rash does not resolve to CTCAE Grade $\leq$ 1 or baseline within 14 days after stopping BIBW 2992 and/or TMZ treatment and despite optimal supportive care, the patient will be taken off drug and off protocol. Exception to this in patients who derive obvious clinical benefit according to the investigator's judgment could be considered upon agreement with BI's Trial Clinical Monitor (TCM).

### **4.3 TREATMENT COMPLIANCE**

The study medications will be given in accordance with the protocol and under the instruction of the investigator at each visit. At all other time points, patients will take the trial drugs at home. Patients will be asked to bring the remaining trial medication at each visit to the investigator for compliance check. The remaining film-coated tablets and/or capsules will be counted by the investigator/site staff and recorded at the study site.

Discrepancies between the number of film-coated tablets and/or capsules taken and the calculated number of film-coated tablets and/or capsules the patient should have taken must be documented and explained. At the end of each treatment cycle leftover medication will be collected.

During the maintenance phase, a maximum of six consecutive doses of BIBW 2992 or seven non-consecutive doses may be missed per cycle (i.e., 28 days) for reasons other than recovery from a drug-related adverse event. These patients will be allowed to continue therapy on the trial. Patients who miss treatment medication more than that are considered non-compliant. Their treatment should be discontinued, and patients will be withdrawn from the study. Patients who discontinue or interrupt the study medication due to AE for less than 14 days are considered compliant.

## 5. OBSERVATIONS

### 5.1 EFFICACY - CLINICAL PHARMACOLOGY OR PHARMACODYNAMICS

#### 5.1.1 Primary endpoints

Determination of the MTD of:

- BIBW 2992 when given concomitantly with radiotherapy (Regimen U)
- BIBW 2992 when given concomitantly with TMZ and radiotherapy (Regimen M)

#### 5.1.2 Secondary endpoints

1. Incidence and intensity of AE according to Common Terminology Criteria (CTCAE v.3, (R06-1666))
2. Objective tumour response rate according to the Macdonald criteria (R08-1053)
3. Pharmacokinetics of BIBW 2992 (Sections 5.5 and 7.3.5).

#### 5.1.3 Tumour assessment

Response will be evaluated according to the Macdonald criteria (R08-1053):

Complete Response (CR): Disappearance of all enhancing tumour on consecutive MRI scans at least 28 days apart, off steroids, and neurologically stable or improved.

Partial Response (PR): At least 50% reduction in size of enhancing tumour on consecutive MRI scans at least 28 days apart, steroids stable or reduced, and neurologically stable or improved.

Progressive Disease (PD): a) at least 25% increase in size of enhancing tumour or  
b) any new tumour on MRI scans or  
c) unequivocal neurological deterioration (due to underlying tumour progression and not due to co-morbid event or concurrent medication) with steroids being stable or increased.

Stable Disease (SD): All other situations

‘Size’, will be defined as the tumour’s largest cross-sectional area. Multifocal lesions are defined as PD if any measurable lesion increases by >25%, or if there is an assessment of any evaluable lesion(s) as progressive.

‘Unequivocal neurological deterioration’ will be assessed locally by each investigator. The clinical decline must be attributed to the underlying tumour progression and not due to co-morbidity or concomitant medication.

Objective tumour response rate is defined as the sum of all CRs and PRs as a fraction of all patients. For a detailed time schedule of tumour assessment please refer to the Flow Chart and Section 6 of this protocol.

Pseudo-progression based on imaging parameters only is a common phenomenon in GBM patients after prior radiotherapy. In order to avoid labelling progressive enhancement or oedema which develops immediately after the end of RT as tumour progression, treatment should not be delayed or stopped within 3 months of RT as suggested by the “Canadian GBM Recommendations committee” (R09-6378)

If a patient shows radiological progression on his/her first scan occurring within 2 months post RT, the patient should not stop study medication and be removed from the study. Instead, the patient should stay on the study until the second MRI scan (scheduled at 4 months post RT) confirms the patient has progressed or not. If the course of events shows that true progression indeed occurred, the date of the first increase in tumor size is to be considered as the date of progression.

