### **3.3.1 Inclusion criteria (Regimen U and Regimen M)**

1. Histologically-confirmed WHO Grade IV newly diagnosed malignant glioma.
2. Proven MGMT gene promoter methylation status before determination of MTD in Regimen U only or tumour material available for MGMT testing unless MGMT test results already available
3. Available early postoperative Gd-enhanced MRI (within 72 hours after initial surgery). In case a patient did not perform a Gd-enhanced MRI within 72 hours post surgery, a Gd-MRI is to be performed prior to start of study treatment.
4. Age  $\geq 18$  years and  $< 70$  years at entry
5. KPS  $\geq 70\%$
6. Patients receiving corticosteroids have to receive a stable or decreasing dose for at least 14 days before start of treatment.
7. Written informed consent that is consistent with local law and ICH-GCP guidelines.

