## **5.6 BIOMARKER - PHARMACODYNAMIC SAMPLING**

### **5.6.1 Methods and timing of sample collection**

#### **5.6.1.1 Tumour samples**

Tumour samples from enrolled patients will be collected as early as possible after informed consent 1 have been obtained. They will need to be sent to a central laboratory for methylation MGMT promotor status determination. Only tumour slices from open surgery are suitable (4 x 10 micron slices).

**Note:** If a patient already has proven MGMT promotor methylation status prior to screening and the test performed by the same laboratory used in the 1200.38 study, the patient will be able to enter in the study without re-testing.

For patients who received trial medication for more than a year:

Archived tumour samples may be collected after informed consent has been obtained. Samples can date back to surgery and/or biopsy. Block or tumour slices (11 x 4 micron slices) are suitable. No new biopsy or surgery will be required for this purpose.

All tumour specimens must be adequately labeled by the Pathology Department providing the specimen for analysis.

Details with regards to tissue collection, labeling and shipping instruction can be found in the ISF at each investigational site.

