### Target volumes

The target volume is to be defined on post-operative planning CT/MRI together with pre-operative images. For enhancing tumours, the CTV is defined as the region of enhancement using the combination of the two sets of images. The PTV will be defined as the CTV with a margin of between 2 and 5cm, based on local practice although it is recommended that a standard 3cm margin is used around the CTV. For unenhancing tumours, the CTV should comprise the region of low intensity on T1 and high signal intensity on T2 and FLAIR sequences (low attenuation on CT). The PTV is defined as the CTV with a margin of 2 to 4 cm although it is recommended 2cm is used. For patients with a presumed transformed glioma which has both enhancing and unenhancing components, the CTV should be as for unenhancing tumours, including the full extent of the disease. In patients who have had complete macroscopic resection of the tumour, the CTV should be estimated from preoperative CT/MRI appropriately adjusted for a recognized shift due to resolution of a mass effect. In practice the CTV should at least cover the full excision cavity margins (not necessarily margins which would have been away from the primary tumour). The CTV – PTV margin should be as specified for unenhancing and enhancing tumours. In all instances the PTV should be adjusted/reduced when traversed by anatomical barriers to tumour migration and spread, such as the skull, falx or tentorium. This should therefore lead to outlining of volume to avoid extension into the orbit and below the cranial cavity beyond that necessary to account for immobilization and machine uncertainties. It is recommended that the same volume is used throughout the course of treatment

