7. PLANNED ANALYSIS

For end of text tables, unless otherwise specified, the set of summary statistics is: N, mean, standard deviation (SD), minimum, median and maximum.

Tabulations of frequencies for categorical data will include all possible categories and will display the number of observations in a category as well as the percentage (%) relative to the respective treatment group. Percentages will be given in whole numbers. The category missing will be displayed only if there are actually missing values. Unless otherwise specified, percentages will be based on all patients in the respective patient set whether they have non-missing values or not.

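### The objective response rate counts all patients, including those with no enhancing tumour at baseline, who cannot reach PR and whose clean scans may be read as SD or CR

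*Protocol*

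**What the plan says.** **Definition.** Protocol 5.1.3 gives the rate: "Objective tumour response rate is defined as the sum of all CRs and PRs as a fraction of all patients". CR is "Disappearance of all enhancing tumour on consecutive MRI scans at least 28 days apart, off steroids, and neurologically stable or improved". PR begins "At least 50% reduction in size of enhancing tumour on consecutive MRI scans at least 28 days apart" and adds steroid and neurological conditions. The remaining class is "Stable Disease (SD): All other situations". There is no class for patients who are not evaluable or have no enhancing disease at baseline.

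**Who enters.** Inclusion criterion 1 (Protocol 3.3.1) is histological. Criterion 3 asks for a postoperative Gd-MRI, within 72 hours of surgery or otherwise before treatment, but sets no condition on what it shows. Exclusion criterion 1 keeps out patients less than two weeks from resection, and the flow charts place radiotherapy 2 to 6 weeks after surgery. Protocol 10.6 provides for complete resection, "In patients who have had complete macroscopic resection of the tumour, the CTV should be estimated from preoperative CT/MRI", and separately for unenhancing tumours.

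**Denominator.** Protocol 7.3 puts every treated patient in the efficacy analysis. SAP 6.3 uses the treated set for all analyses. Under SAP 7, unless otherwise specified, "percentages will be based on all patients in the respective patient set whether they have non-missing values or not". SAP 5.2.3 defines objective response as a best overall response of CR or PR, without clinical disease assessment and up to progression or further anti-cancer treatment. It has no rule for patients without enhancing tumour at baseline.

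**The concern.** The Macdonald categories describe change in enhancing tumour. Where there is none at the start, the endpoint has nothing to measure, yet the patient stays in the denominator. Nothing visible in either document settles how that patient is scored. The same scans can therefore count as a non-response or as a complete response, depending on the reader.

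Objective response is the only efficacy criterion in the synopsis and the only efficacy item among the secondary endpoints. If the plan is followed exactly, the reported rate is either diluted by patients who could not respond or inflated by patients whose tumour was removed by surgery. A later reader could not correct for this, because the tumour history listed in Protocol 5.3.1 covers the date of diagnosis and the location, not the extent of resection.

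**Working it through.** The plan states no response rate, target or power for this endpoint, so there is no figure of its own to reproduce here. The sample-size arithmetic in Protocol 7.6, 2 × (12 + 6 + 6) = 48, is correct and does not depend on this point.

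**Step 1: scoring from a zero baseline.**
- PR needs a reduction of at least 50% in the size of enhancing tumour. No reduction from zero is possible, so PR cannot be assigned.
- CR speaks of disappearance. Consecutive clean scans meet this if the test is that nothing is seen, and fail it if something must first have been there.
- If CR is refused and there is no progression, the patient falls into SD, the residual class.
- PD remains assessable, because any new tumour on MRI counts.

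**Step 2: effect on the rate.** Let f be the share of treated patients with no enhancing tumour at baseline, and p the response rate in the others. Both are assumptions, as neither document gives them.
- Clean scans scored SD: rate = p(1-f).
- Clean scans all scored CR: rate = p(1-f) + f.
- The two readings differ by exactly f.

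With p = 20%:

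| f | Scored SD | All scored CR (upper bound) |
|---|---|---|
| 10% | 0.20 × 0.90 = 18% | 18% + 10% = 28% |
| 30% | 0.20 × 0.70 = 14% | 14% + 30% = 44% |
| 50% | 0.20 × 0.50 = 10% | 10% + 50% = 60% |

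With p = 10%, the range is 9% against 19% at f = 10%, and 5% against 55% at f = 50%. With p = 30%, it is 27% against 37%, and 15% against 65%.

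**Step 3: one expanded MTD cohort of 12.** Assume 4 patients with no enhancing tumour at baseline and 1 true responder among the other 8. Exact 95% intervals are in brackets.
- All patients, the 4 scored SD: 1/12 = 8% (0.2% to 38.5%).
- All patients, the 4 scored CR: 5/12 = 42% (15.2% to 72.3%).
- Patients with enhancing tumour at baseline: 1/8 = 12.5% (0.3% to 52.7%).

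The intervals are wide under any rule, but the move from 1/12 to 5/12 comes from labelling alone.

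**Step 4: why the CR column is a ceiling.** It needs every patient without enhancing tumour to be called CR. Protocol 5.1.3 also requires such a patient to be off steroids, neurologically stable or improved, and clean on consecutive scans at least 28 days apart. Patients who progress or leave early would not qualify.

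**The case against.** The strongest reply is that little turns on this endpoint. It is secondary and descriptive. Protocol 7.2 plans no hypothesis test, and 7.3 rules out comparisons between regimens or cohorts. This stands, and it limits the consequence.

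A reader might infer from Protocol 7.1, which says preliminary therapeutic effects help identify the optimal dose, that a chance imbalance in resection could be mistaken for a dose effect and mislead the dose choice. The documents do not support that. Protocol 7.3.1 bases the MTD and the recommended dosage on DLTs. Section 7.3.4 bases its dose recommendation on DLT incidence and further safety observations. No stated rule takes the response rate as an input. In addition, all cohorts are planned to receive 40 mg/day after radiotherapy (4.1.4.1), apart from case-by-case decisions for dose-reduced patients. The first scheduled response MRI comes about 7 to 8 weeks into that phase: 28 + 21 to 28 + 28 days, counting Cycle 1 and then Cycle 2 in Regimen U, or the TMZ break and then Cycle 1 in Regimen M.

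A reader might also infer that the rate will mainly reflect how many patients were completely resected. That is not shown. The share is unknown. Protocol 10.6 foresees complete resection but gives no frequency, and complete macroscopic resection is not defined there as absence of MRI enhancement. Requiring tissue from open surgery (5.6.1.1) does not imply complete resection either. The word disappearance favours the SD reading, under which the error is dilution.

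Two further points stand in part. Protocol 7.3.2.1 tabulates CR, PR, SD and PD separately, so an unexpected excess of CRs would be visible, though not explained. Parts of the SAP are blacked out, so a rule there cannot be excluded. The visible sections on the endpoint, the analysis set and percentages contain none.

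**Conclusion.** The point holds as a defect in how a descriptive secondary endpoint can be interpreted. The stated denominator includes patients who cannot reach PR, and the visible text does not decide between SD and CR for them. Under SD the rate is diluted by the factor 1-f. Under CR it exceeds the SD figure by up to f. With an assumed f of 10% to 50% and an assumed 20% response rate in the others, that is 18% down to 10% under SD, and at most 28% up to 60% under CR.

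The MTD, the sample size and every stated decision rule are unaffected. The textual gap is certain in what can be read. Its size rests on assumed values of f and p, and on no rule lying in the redacted parts of the SAP.

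**What to change.** In Protocol 5.1.3 and 7.3.2.1 and in SAP 5.2.3 and 7.5.2:

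1. State that CR and PR cannot be assigned to a patient with no enhancing tumour on the last Gd-MRI before treatment.
2. Report the response rate among treated patients with enhancing tumour at baseline, with counts per regimen and cohort, beside the all-treated rate under the same rule.
3. Report the remaining patients as progressed or not progressed.

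The rule should be fixed before database lock, because the trial is open-label and labelling case by case should be avoided.

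**Cost.** Wording changes and one baseline flag. The Gd-MRI is already required, and Macdonald scoring already needs the baseline size of enhancing tumour. No visible text shows that size being recorded as data, so a CRF field may be needed. No visit, scan or treatment changes.

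**Downsides.** Denominators become small: in a cohort of 3, only 1 or 2 patients, or none, may have enhancing tumour at baseline. If the only baseline scan is the one taken within 72 hours of surgery, regrowth before treatment starts 2 to 6 weeks after surgery could be missed and the patient misclassified. Showing both rates with their counts keeps these limits visible.

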## **5.2 SAFETY**

### **5.2.1 Adverse events**

Upon inclusion into the trial, the patient’s condition is assessed (e.g., documentation of history / concomitant diagnoses and diseases), and all relevant changes from baseline are noted subsequently.

AEs will be collected from the date of signature of informed consent number 2. Once the MTD in Regimen U is determined, AEs will be collected from the date of signature of informed consent number 3.

Patients will be required to report spontaneously any adverse events (AEs) as well as the dates of onset and end of these events. These include all events that affect the well-being of the patients irrespective their relatedness to the treatment. Specific questions will be asked wherever required or useful to more precisely describe an AE and to allow a grading according to CTCAE, Version 3 (R06-1666).

A carefully written record of all AEs shall be kept by the investigator in charge of the trial. Records of AEs shall include data on the date of onset, end date and CTCAE grading of the event as well as any treatment or action required for the event and its outcome.

Regular and continuing assessment of safety will be performed for both parts of the study as outlined in the Flow Chart of this protocol. A dose reduction scheme is provided in Section 4.1.4.1.2 for patients who experience specified adverse events and who, at the discretion of the investigator, could derive benefit from continuing treatment on the protocol.

Adverse events with an onset during therapy with trial medication or within 28 days after discontinuation of drug intake are considered as “on-treatment”. Adverse events which are not yet recovered at the EOT visit will be followed up until recovery or in case of persistence sufficient characterization of the toxic effects has been achieved and the investigator and

Boehringer Ingelheim agree not to pursue them further. Adverse events that occur more than 28 days after last administration of study drug will only be reported if they are considered drug- or trial procedure-related.

Definitions and requirements for documentation and reporting of AEs and serious adverse events (SAEs) are provided in Sections 8.4.1. A list of expected adverse events with BIBW 2992 can be found in the current version of the investigator brochure.

The EU prescribing information for Temozolomide (current SPC) will be used for assessment of international listedness/expectedness of temozolomide.

Hospitalizations for administrative reasons or hospitalizations already planned prior to informed consent need not be reported as an SAE, unless other serious criteria are met.

Changes in safety tests including blood pressure, pulse rate, electrocardiogram (ECG) and laboratory tests will be recorded as AEs, if they are not associated with an already reported AE, symptom or diagnosis, and:

- action is required and taken with the investigational drug, i.e., dose reduction or treatment discontinuation, or
- treatment is required (i.e., a concomitant medication is added or changed).

Specific secondary safety-related endpoints are defined in Section 7.3.3

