-  Visit frequency will be as follows: every month for the first 6 months after RT (C1 to C6), every 2 months thereafter for the next six months (C8,C10,C12) and then every three months for the following year (C15,C18,C21, C24), and every 6 months thereafter (C30, C36.....). During the maintenance treatment phase visits should be performed as scheduled wherever possible, but within 2 days of the schedule date.
-  EOT: end of treatment visit; within 5 calendar days after permanent termination of trial drug intake. Investigations to be performed instead of the scheduled visit when a patient discontinues study treatment permanently. If permanent discontinuation of study drug falls on a scheduled visit, examinations as defined for EOT should be performed instead of the examinations of the scheduled visit.
-  FU: Follow-up visit: 28 days ( $\pm 4$ ) after EOT.
-  Early postoperative MRI (within 72 hours after initial surgery) preferable. In case a patient did not perform a Gd-enhanced MRI within 72 hours post surgery, a Gd-MRI is to be performed prior to start of study treatment MRIs should be performed between day 21 and day 28 of Cycle 2, 4, 6, 8, 10 and 12. In the second year, MRIs are performed every 3 months (Cycle 15, 18, 21, 24) and every six months thereafter (Cycle 30, 36...). The EOT MRI/tumour assessments are not required if performed in the previous 4 weeks.
-  For women of childbearing potential only.
-  Same method (Echo or MUGA) must be performed throughout study.
-  Includes height (at screening only) and weight.
-  ECG will be performed at Cycle 2 and every 8 weeks thereafter until cycle 12 (Cycle 4, 6, 8, 10, 12.) and then every three months for the following year (C15, C18, C21, C24), and every 6 months thereafter (C30, C36.....).
-  MMSE will be repeated at Cycle 2, 4, 6, 8,10 ,12 and then every three months for the following year (C15, C18, C21, C24), and every 6 months thereafter (C30, C36.....).
-  Includes CBC, serum biochemistry, and urinalysis, see Section 5.2.6 for details.
-  If not recovered at EOT, or new drug related AE
-  For detailed timing refer to Section 5.5.1 and 10.1
-  RT should be performed between 2 weeks and 6 weeks post surgery

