### 4.1.4.1.2 Dose reduction scheme for BIBW: Regimen U and M

If a patient develops side effect that meets criteria for DLT (for definition refer to Section 5.2.3) regardless of treatment cycle, treatment with BIBW 2992 must be paused. If all drug-related adverse events recover to CTCAE Grade 1 or baseline (whichever is higher) within 14 days of stopping treatment with BIBW 2992, treatment may be resumed with dose reductions according to Table 4.1.4.1.2: 1. Otherwise, the patient will be taken off study. Exceptions to this are patients who derive obvious clinical benefit according to the investigator's judgment. These patients could be considered in agreement with BI's Trial Clinical Monitor (TCM) for further treatment.

If a patient need to dose reduced BIBW 2992 during RT, the dose of BIBW 2992 during the maintenance period will need to be discussed and decided on a case to case base between BI Trial Clinical Monitor and the investigator at site (keep BIBW2992 reduced daily dose or change as planned for 40mg BIBW2992 daily)

Table 4.1.4.1.2: 1 Dose reduction scheme for Regimen M and U

Treatment prior to treatment pause and dose reduction BIBW (mg)	Dose reduction		
	1 st DLT BIBW (mg)	2 nd DLT BIBW (mg)	3 rd DLT
20	Off-study		
30	20	Off-study	
40	30	20	Off-study

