### 5.2.3 Dose-limiting Toxicity (DLT)

A dose-limiting toxicity (DLT) is defined as an adverse event or laboratory abnormality that is: a) considered to be related to BIBW 2992 as used in regimen U or M and b) meets any of the following criteria:

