5. ENDPOINTS

5.1 PRIMARY ENDPOINTS

Investigator defined dose limiting toxicity during concomitant treatment period:

At least one AE meeting the criteria for dose limiting toxicity (DLT; as determined by the investigator and defined in Section 5.2.3 of the CTP) with onset during the 42 day concomitant treatment period when trial medication is given concomitantly with radiotherapy (RT).

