7.8.4 ECG

This section is not applicable because only limited ECG data are collected. Clinically relevant ECG findings will be reported as AEs.

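### The SAP relies on AE records for ECG findings and DLTs, but Protocol 5.2.1 ties AE recording of test changes to action taken, and the Protocol 7.3.1 listing of DLT-grade laboratory abnormalities is dropped

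*Protocol*

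**What the plan says.** **Recording rule.** Protocol 5.2.1 covers changes in blood pressure, pulse rate, ECG and laboratory tests. They become AEs "if they are not associated with an already reported AE, symptom or diagnosis", provided also that one of two conditions holds: "action is required and taken with the investigational drug, i.e., dose reduction or treatment discontinuation", or a treatment is needed, meaning a concomitant drug started or altered.

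**DLT definition and primary table.** Protocol 5.2.3 opens: "A dose-limiting toxicity (DLT) is defined as an adverse event or laboratory abnormality that is" related to BIBW 2992 and meets a listed criterion. Protocol 7.3.1 asks for a table of every AE and laboratory abnormality that meets those criteria, related or not, showing for each whether it was judged a DLT.

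**Action after a DLT.** Under Protocol 4.1.4.1.2, "regardless of treatment cycle, treatment with BIBW 2992 must be paused". The patient then resumes at a reduced dose or leaves the study, with an exception for obvious clinical benefit. Protocol 5.2.5 classes DLTs as significant AEs, and 8.4.1 requires those to be reported immediately.

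**SAP.** Section 5.1 defines the primary endpoint as "At least one AE meeting the criteria for dose limiting toxicity", as determined by the investigator, with onset in the 42-day concomitant period. Section 7.4 summarises AE occurrences that the investigator called DLTs. Section 7.8.4 plans no ECG analysis because "only limited ECG data are collected. Clinically relevant ECG findings will be reported as AEs". Section 4, which lists departures from the protocol's analysis, mentions neither the loss of laboratory abnormalities from the endpoint nor the loss of the 7.3.1 listing.

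**The concern.** The SAP uses the AE database as its only route to two things: ECG findings and DLTs. The protocol does not fill that database on the terms the SAP assumes. For ECGs, the SAP expects entry on clinical relevance, while the protocol requires action on the drug or a new treatment. For laboratory DLTs, the protocol counts the abnormality itself and asks for a listing that does not depend on the investigator's attribution, while the SAP starts from AEs already labelled as DLTs.

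Two things are at stake. ECG data collected throughout treatment could go largely unreported. And the primary endpoint turns on single patients, so a qualifying laboratory value that never became an AE would make a dose look safer than it was.

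**Working it through.** **1. Which test changes depend on AE status?** Of the four kinds of test named in Protocol 5.2.1, three have their own analysis:

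| Test change | Analysis outside AEs |
|---|---|
| Laboratory | Change from baseline (Protocol 7.3.3); clinically significant abnormalities by sponsor standard (SAP 4); descriptive (SAP 7.8.2) |
| Blood pressure, pulse | Descriptive (SAP 7.8.3) |
| ECG | None (SAP 7.8.4) |

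Only ECG changes rest entirely on the AE route.

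**2. ECG.** The test in Protocol 5.2.1 is action taken; the test in SAP 7.8.4 is clinical relevance. A relevant ECG change with no dose reduction, discontinuation or treatment, and no linked event, fails the first and passes the second. It is then in no planned output.

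Scheduled on-treatment ECGs per patient through cycle 12, excluding screening and EOT:
- Regimen U: Day 8, then "ECG will be performed at Cycle 2 and every 8 weeks thereafter until cycle 12", which is cycles 2, 4, 6, 8, 10 and 12. 1 + 6 = 7.
- Regimen M: Day 8, Day 70, and cycles 1, 3, 5, 8, 10 and 12. 2 + 6 = 8.

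These are ceilings for patients still on treatment at cycle 12. With 28-day cycles that visit falls near Day 42 + 12 × 28 = 378 in Regimen U and Day 70 + 12 × 28 = 406 in Regimen M, slightly beyond one year.

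**3. Laboratory DLTs.** A recognised laboratory DLT has two routes into the AE data. The reduction or off-study step in 4.1.4.1.2 fires the first condition of 5.2.1, and 5.2.5 with 8.4.1 requires a significant-AE report. Both routes start from recognition. Three cases can fall outside them:
- *Not recognised.* Nothing starts the pause or the report. Grade 2 creatinine or proteinuria (5.2.3) may prompt no treatment. Growth factors and transfusions are restricted during chemoradiation (4.2), so for a cytopenia the treatment condition is less likely to fire.
- *Judged unrelated.* This is not a DLT under 5.2.3, but the 7.3.1 listing would have let a reader see the attribution.
- *Clinical-benefit exception.* This is narrow: Protocol 6.3 directs that the reduction table still be followed, although that table has no tier below 20 mg, and 5.2.5 still applies. It matters only if a site follows 5.2.1 rather than 5.2.5.

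The 7.3.1 table, drawn from laboratory data as well as AEs, was the independent check on these cases. Descriptive laboratory summaries do not feed the DLT count.

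**4. What a miss would do.** Under Protocol 5.2.4, 1/6 = 16.7% is acceptable and 2/6 = 33.3% is not, so one unrecorded DLT can change the result. To show direction, let p be the true DLT rate and m the share unrecorded, both assumed because the documents give neither. With q = p(1 − m), the chance of escalating past a dose (0/3, or 1/3 then 0/3) is (1 − q)³ + 3q(1 − q)⁵:

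| p | m = 0 | 10% | 20% | 30% |
|---|---|---|---|---|
| 0.17 | 0.773 | 0.808 | 0.841 | 0.873 |
| 0.25 | 0.600 | 0.654 | 0.709 | 0.762 |
| 0.33 | 0.434 | 0.500 | 0.570 | 0.641 |

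For p = 0.33 and m = 0: 0.67³ + 3 × 0.33 × 0.67⁵ = 0.301 + 0.134 = 0.434 after rounding of the unrounded sum. Only DLTs that are purely laboratory findings are exposed, and their share is not given.

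**The case against.** The case for leaving the plan alone has real force.

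- *Laboratory data are not lost.* A reader might infer that unactioned laboratory changes are reported nowhere. That is wrong, as step 1 shows. How far the sponsor's laboratory standard would flag DLT-grade values cannot be seen from the documents.
- *Recognised DLTs are captured.* A reader might picture a DLT found on Day 42, a pause, and then the planned 40 mg in maintenance, leaving no AE. The documents do not support this. The case-by-case clause in 4.1.4.1.2 is for patients whose dose was already reduced during RT, and that reduction is itself recordable. Ignoring the reduction scheme after a DLT is important protocol violation C4.1 in SAP Table 6.2: 1.
- *Escalation is decided during the trial.* It follows 4.1.4.1.1, using the 5.2.3 definition and with sponsor agreement, and does not wait for SAP tables. This stands for cohort decisions. But Protocol 7.3.1 and SAP 7.4 both give the DLT analysis the aim of determining the MTD, so the reported result still depends on what is counted.
- *A pause may already count.* Protocol 4.2.3 (rash) and 4.3 use discontinuation for temporary stops. The wording in 5.2.1 is therefore ambiguous, not a clear exclusion.
- *ECG data may indeed be limited.* Only one on-treatment ECG falls within the 42-day period, the eCRF content is not shown, and ECG changes with symptoms or a diagnosis are AEs anyway. This reduces the number affected but does not make the SAP's premise true. A reader might also cite the minipig QT finding in Protocol 1.2.1. That section concludes that the data indicate no risk of QT-prolongation arrhythmia, so the point rests on the mismatch alone.

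**Conclusion.** The concern holds in a limited form. The reason SAP 7.8.4 gives for omitting ECG analysis is not secured by Protocol 5.2.1, and unactioned ECG changes without a linked event have no planned analysis. SAP 5.1 and 7.4 narrow the protocol's primary analysis without declaring it. Amendment 3, to which SAP 4 refers, does not explain this on the text available: the current protocol already mentions amendment 5 and still contains the fuller 7.3.1.

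The laboratory gap is small: values that met a criterion but were not recognised, were judged unrelated, or fell under the clinical-benefit exception. Any missed DLT favours the dose, and one patient in six is enough to matter. The documents do not show that such misses would occur or how often, and the probabilities above illustrate direction only. This is an alignment fault in the primary analysis and the ECG reporting, not evidence that the MTD would be wrong.

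**What to change.** 1. **SAP 5.1 and 7.4.** Define the endpoint on an AE or laboratory abnormality, as Protocol 5.2.3 does. Restore the 7.3.1 listing of all AEs and CTCAE-graded laboratory values that meet a 5.2.3 criterion, irrespective of relatedness, with the investigator's DLT judgement shown beside each.
2. **Protocol 5.2.1.** Reconcile it with 5.2.3, 5.2.5 and SAP 7.8.4, so that a change meeting a 5.2.3 criterion, or judged clinically relevant by the investigator, is recorded as an AE whatever was done about it. State whether a pause counts as action. This concerns recording only and changes no dosing rule.
3. **SAP 7.8.4.** Replace the not-applicable statement with a listing or count, by cohort, of patients with a clinically relevant ECG change from screening.

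The cost is a few more AE records, one listing and one small table. The laboratory tests and ECGs are already scheduled. If the ECG interpretation is not held in the eCRF, which the documents do not show, item 3 would also need that field.
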